### **3.2.3 ANALYSIS OF PRIMARY EFFICACY ENDPOINT**

The primary efficacy endpoint is the percentage of subjects with the event of requiring hospitalization, emergency room visits, or resulting in death due to progression of CAP related to SARS-CoV-2 or influenza. For subjects terminated the study that event observation stopped before Day 29 and no event is observed, the subjects will be counted as 'Treatment Fail'.

The primary endpoint will be summarized in number of subjects and percentage with corresponding Clopper-Pearson exact 95% CI. Fisher's exact test or Cochran-Mantel-Haenszel test will be applied. In addition, 95% CI of treatment difference in event rate will be presented in normal approximation. Event rate including Treatment Fail rate will be tested additionally for sensitivity analysis defined in section 3.2.9.

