5.2.5.6. Hospitalization events

If a subject is admitted to the hospital, the participant will remain in the study and follow the procedures outlined in the visit schedule. Hospitalization is defined as inpatient admission.

The date of hospitalization events will be recorded in the CRF and includes:

- Hospitalization
- Emergency room visit: only for dosed subjects that last 24 hours or longer will be included
- ICU admittance
- Extended care facility (ECF) admittance: ECF events will only be documented for subjects dosed in the trial who experience adverse events (AEs) and require additional medical support in the ECF, such as respiratory therapy to address the AEs. The requirement for additional medical support in the ECF is considered comparable to hospitalization as a discretion by the investigator. This means ECF events occurring before trial enrollment will not be documented. Additionally, enrolled subjects without experiencing AEs move to the ECF after enrollment will not be considered hospitalized and do not need to be entered into the EDC.
- Discharge

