### **3 STATISTICAL CONSIDERATIONS**

#### **3.1 ANALYSIS POPULATION**

The following populations will be introduced for statistical analysis.

Analysis population	Description
Intent-to-Treat (ITT) Population	All randomized subjects who receive at least one dose of CX-4945 or placebo
Per-Protocol (PP) Population	

• The set of subjects who meet the ITT population

• Receive 80 - 120% of 10 doses of the IP during Days 1 - 6 or die before Day 6

• Not associated with any major protocol violations that have impact on efficacy evaluation

Modified Per-Protocol (mPP) Population =Evaluable subjects	

• The set of subjects who meet the ITT population

• Receive 80 - 120% of 10 doses of the IP during Days 1 - 6 or die before Day 6

• Complete the required visits by Visit 4 or die before Visit 4

• Not associated with any major protocol violations that have impact on efficacy evaluation by Visit 4

ITT population will be used as the primary analysis population for efficacy endpoints and the analysis population for baseline data, safety and exploratory endpoints. PP population will also be applied on AE analysis. PP and mPP populations will be used as the supportive analysis population for efficacy endpoints.

All analyses will be performed on actual treatment taken unless otherwise specified. For PP and mPP populations, all inclusion and exclusion criteria should be fulfilled as applied in the latest version.

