### **3.3.2 HANDLING OF DROPOUTS OR MISSING DATA**

For primary efficacy endpoint and secondary points that is the percentage of subjects with all cause hospitalization, emergency room visit or death during study period, the subject will be counted as ‘Treatment Fail’ when subject has been terminated the study and event observation has been stopped before Day 29 with no event observed.

For by-visit efficacy endpoints, ITT analyses applying LOCF (Last Observation Carry Forward) data imputation will be performed additionally as a sensitivity analysis.

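### The main and sensitivity analyses of the primary endpoint impute early terminators in the same direction in both arms, so together they do not bound the treatment difference

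*SAP*

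**What the plan says.** SAP 3.2.3 defines the label: a subject who terminated the study, where "event observation stopped before Day 29 and no event is observed", is counted as Treatment Fail. SAP 3.3.2 repeats the rule for the primary endpoint and for the all-cause composite of hospitalization, emergency room visit or death, with the two conditions joined: the label applies "when subject has been terminated the study and event observation has been stopped before Day 29 with no event observed".

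The label is used in one place: "Event rate including Treatment Fail rate will be tested additionally for sensitivity analysis". SAP 3.2.11 confirms this for both composites. The effect measure is the difference in event rates: "95% CI of treatment difference in event rate will be presented in normal approximation", alongside Fisher's exact test or Cochran-Mantel-Haenszel.

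On the population, SAP 3.1 says that "ITT population will be used as the primary analysis population for efficacy endpoints". SAP 3.2.3 itself does not name the denominator of the main event rate.

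Protocol 3.5 says that no further medical information is sought after withdrawal, so the Day 29 outcome of these subjects stays unknown. It also requires the date of a premature withdrawal to be documented. Protocol 5.2.5.6 adds: "The date of hospitalization events will be recorded in the CRF".

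**The concern.** A missing-outcome sensitivity analysis should show how far the treatment comparison could move if the unobserved outcomes differed from what the main analysis assumes. Here both analyses make one assumption for everyone: no early terminator has an event, or every one does. That brackets the event rate within each arm. It does not bracket the difference between arms, because the extreme cases for a difference arise when the missing outcomes go one way on CX-4945 and the other way on placebo.

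The risk is false reassurance. If losses are similar in the two arms, the report will show nearly the same difference twice, and a reader may conclude that missing outcomes do not matter when the pair has not tested that.

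No other planned analysis fills the gap. LOCF applies only to by-visit endpoints (SAP 3.2.11). The PP and mPP sets select on dosing, protocol violations and, for mPP, visits through Visit 4; they do not address an unknown Day 29 outcome. No planned analysis of this endpoint uses partial follow-up, so a subject lost event-free on Day 3 and one lost event-free on Day 20 are treated alike.

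**Working it through.** **Inputs from the documents.** 44 subjects randomized (SAP 3.4.1); 1:1 allocation in each domain (SAP 2.1); difference in event rates as the effect measure (SAP 3.2.3).

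**Inputs assumed.** 22 per arm (44/2 under 1:1), event counts and numbers of early terminators. The documents give none of these by arm. SAP 3.4.1 says only that events were too few for logistic regression.

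**The plan's own figure.** The only derived number nearby is the enrolment target. 120 evaluable over four arms is 30 per arm; 30/0.90 = 33.3, rounded up to 34; 34 × 4 = 136, as stated. The documents give no event rate, treatment difference or early-termination rate to reproduce.

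**Formulas.** Let eT and eC be observed events, mT and mC event-free early terminators, and n the arm size. Differences are CX-4945 minus placebo, so negative values favour CX-4945.

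- Main analysis: D = (eT − eC)/n
- Treatment Fail analysis: [(eT + mT) − (eC + mC)]/n = D + (mT − mC)/n
- Lowest value the data allow (only placebo losses have events): D − mC/n
- Highest value the data allow (only CX-4945 losses have events): D + mT/n

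The planned pair spans |mT − mC|/n. The possible range is (mT + mC)/n wide. The two are equal only when one arm has no losses; with equal losses the pair spans zero.

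**Numbers.** Take n = 22, eT = 1, eC = 3, so D = (1 − 3)/22 = −9.1 points. With 3 losses per arm, for example, the Treatment Fail difference is (4 − 6)/22 = −9.1, the lower limit (1 − 6)/22 = −22.7 and the upper limit (4 − 3)/22 = +4.5.

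| Losses mT / mC | Main | Treatment Fail analysis | Possible range |
|---|---|---|---|
| 1 / 1 | −9.1 | −9.1 | −13.6 to −4.5 |
| 2 / 2 | −9.1 | −9.1 | −18.2 to 0.0 |
| 3 / 3 | −9.1 | −9.1 | −22.7 to +4.5 |
| 4 / 4 | −9.1 | −9.1 | −27.3 to +9.1 |
| 3 / 1 | −9.1 | 0.0 | −13.6 to +4.5 |
| 1 / 3 | −9.1 | −18.2 | −22.7 to −4.5 |

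With 4 losses per arm, Fisher's exact p is 0.61 and 0.74 for the planned pair, but 0.046 and 0.70 at the two limits.

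**The case against.** **The planned analysis does respond to dropout.** A reader might infer that the sensitivity analysis cannot reveal any sensitivity to dropout. That goes too far: the last two rows of the table show it moving by (mT − mC)/n when losses differ, and if only one arm loses subjects the pair spans the possible range exactly. What stands is that it falls short whenever both arms lose subjects.

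**Sampling error is larger anyway.** With 3 losses per arm, the normal-approximation intervals are −25.9 to +7.7 (main) and −33.7 to +15.5 (Treatment Fail), and both contain the whole −22.7 to +4.5 range. This is fair for a trial of 44. But those intervals describe sampling error given one imputation. The corresponding intervals at the two limits are −43.3 to −2.2 and −17.0 to +26.1, which together reach beyond either planned interval.

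**Little rests on the comparison.** The study is described as exploratory, was not sized on power, has no primary hypothesis and stopped early. That limits the consequence. It does not change what the pair can show.

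**Some partial checks exist.** Events seen before withdrawal do count, and mPP removes non-fatal cases with incomplete visits through Visit 4. Neither bounds the difference.

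**Two further inferences that the documents do not support.** A reader might think the Day 29 cut-off turns completers seen on Day 26–28, inside the Visit 5 window of Day 29 ± 3, into failures. But the rule is limited to subjects who terminated the study, SAP 3.3.2 makes the two conditions joint, and SAP 3.2.8 counts completed and discontinued subjects separately. A reader might also take the plan's 10% attrition as an early-termination rate and work out how many sensitivity failures would be dropouts. That 10% is loss from the evaluable (mPP) set, which also excludes subjects for dosing, violations and missed visits, so it cannot be used that way.

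**Conclusion.** The point holds as a limitation of the missing-outcome plan for the primary endpoint, and equally for the all-cause composite, which is analysed the same way. The planned pair bounds each arm's rate but, when both arms have early terminators, not the treatment difference. At an assumed 22 per arm with events 1 vs 3, two losses per arm leave an 18.2-point range that the pair reports as zero width; three per arm leave 27.3 points and allow the sign to reverse.

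This rests on reading the main denominator as all ITT subjects, which is implied rather than stated, and on assumed event and loss counts. The algebra does not depend on those counts, but the size does. If few or no subjects terminated early, the effect is negligible. It is a change worth making, not a fault that invalidates the analysis.

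**What to change.** In SAP 3.2.11, for the primary endpoint and the all-cause composite:

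- Add arm-opposed imputation: early terminators count as events on CX-4945 only, then on placebo only. Report the difference and 95% CI for each.
- Add a supportive Kaplan-Meier estimate of Day 29 event risk per arm, censored at last contact, with the difference and 95% CI. This uses the follow-up actually observed.
- Report the number of event-free early terminators in each arm, so that the range can be read directly.

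In SAP 3.2.3, state that the denominator of the main event rate is all ITT subjects, and correct the cross-reference for the sensitivity analysis: it points to 3.2.9 (concomitant medications), but the analysis is in 3.2.11. If the data have already been unblinded, label the additions post hoc.

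The cost is a few sentences and a little programming, since hospitalization-event and withdrawal dates are already recorded. Kaplan-Meier assumes non-informative censoring and does not itself bound the difference, which is why it is supportive and the arm-opposed analyses are needed as well.

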7.3. General Consideration

Statistical analyses will be performed using SAS® for Windows, version 9.4 or later. All available data will be displayed via subject data listings, and summarized for each evaluation time point as appropriate by study domain (including domain-pooled) and study arm. The categorical data will be summarized with the number of subjects and percentage. Continuous data will be summarized by descriptive statistics (i.e., number of subjects, mean, standard deviation, minimum, maximum, and median). For by visit (by Day) analyses, the acceptable window for each visit will be defined in the Statistical Analysis Plan (SAP).

In general, categorical data will be analyzed by using Logistic regression (on efficacy data), Fisher's exact test or Cochran-Mantel-Haenszel test stratified by domain for comparing overall treatment group difference (treatment odds ratio for Logistic regression). For by-domain subgroup analysis on efficacy data, categorical data will be tested by using Fisher's exact test or Chi-square test.

Continuous data will be analyzed by using analysis of variance (ANOVA) on baseline data, and by using analysis of covariance (ANCOVA) on change data for comparing overall treatment group difference. Non-parametric method shall be adapted or log-transformation may be needed for non-normally distributed data. For by-domain subgroup analysis on efficacy data, continuous data will be tested by using two-sample t test or Wilcoxon Rank-sum test.

For the ANOVA, ANCOVA model and Logistic regression, factors of treatment, domain (as appropriate), site and baseline value (for post-baseline data) and other baseline factors (for post-baseline efficacy data, to be defined in the SAP, as appropriate) will be included in the model if significant, those non-statistically significant factors except treatment will be removed from the model (alpha=0.1 for interaction, 0.05 for others). The Logistic regression result will be presented with treatment odds ratio and its 95% confidence interval (CI).

All statistical tests will be two-sided and evaluated at the 0.05 level of significance. All confidence intervals, if provided, will be the 95% CI.

The most recent value before first dose administration will be defined as the baseline value; therefore, the baseline value will be the outcome of the closest evaluation performed before or equal to the first dosing date.

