### **3.2.4 ANALYSIS OF SECONDARY EFFICACY ENDPOINT**

#### **The percentage of subjects with all cause hospitalization, emergency room visit or death during study period**

This endpoint will be analyzed in the same way as on primary endpoint.

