#### **3.4.1 STATISTICAL METHODS CHANGE**

Due to early termination of the study, only 44 subjects were randomized. For both the primary and secondary endpoints, the number of events observed prior to unblinding was insufficient to support reliable estimation using logistic regression. Therefore, Logistic regression will not be applied in the analysis.

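### With logistic regression dropped for too few events, the only treatment-effect interval left is a normal approximation that collapses to 0 to 0 if neither arm has an event

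*SAP*

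**What the plan says.** Protocol 7.7.1 analyses the primary endpoint by logistic regression, with Fisher's exact or Cochran-Mantel-Haenszel (CMH) test as the fallback. Protocol 7.3 has the regression reported as a treatment odds ratio with a 95% CI. The normal-approximation interval for the rate difference was an addition to that.

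SAP 3.4.1 withdraws the model. It says that "only 44 subjects were randomized" and that "the number of events observed prior to unblinding was insufficient to support reliable estimation using logistic regression".

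SAP 3.2.3 keeps three outputs:

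- per-arm rates with exact intervals: "The primary endpoint will be summarized in number of subjects and percentage with corresponding Clopper-Pearson exact 95% CI";
- a test: "Fisher's exact test or Cochran-Mantel-Haenszel test will be applied";
- the difference: "In addition, 95% CI of treatment difference in event rate will be presented in normal approximation".

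SAP 3.2.4 carries this to the composite of all-cause hospitalization, emergency room visit or death: "This endpoint will be analyzed in the same way as on primary endpoint". The SAP text gives no variant of the normal approximation, no zero-event rule and no alternative interval for the difference. SAP 3.4 does not revisit it.

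**The concern.** The SAP recognises that events are too sparse for one large-sample method and keeps another in the paragraph that reports the primary endpoint. In that same paragraph it uses exact intervals for the single rates.

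Once the odds ratio is gone, nothing else in the SAP text describes the size and uncertainty of the treatment effect. The Clopper-Pearson intervals each describe one arm, and Fisher and CMH are listed only as tests. If there are no events at all, Fisher gives p = 1 and the CMH statistic is undefined. The interval is then the only between-arm output that could carry information, and it would report perfect certainty that the arms do not differ.

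This matters more because the sample size has no power basis (SAP 2.3), so the primary result is essentially an estimate. SAP 3.2.12 also plans analyses by domain, where numbers are smaller still.

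**Working it through.** **Inputs.** From the documents: 44 randomized (SAP 3.4.1), 1:1 allocation (SAP 2.2), 95% two-sided intervals (SAP 3.2.2). Assumed: 22 per arm, 11 per arm per domain, and all event rates. The documents give none of these. The only sizing figure is about 136 enrolled for 120 evaluable; it is reproduced by rounding up in four arms of 30, 4 × ⌈30/0.9⌉ = 136. It involves no event rate, so there is no planned precision to compare with.

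**No events in either arm, 0/22 vs 0/22.** With z² = 3.8415:

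- Wald: d ± 1.96·√[p₁(1−p₁)/n₁ + p₂(1−p₂)/n₂]. Both variance terms are 0, so the interval is 0 to 0 at any sample size.
- Clopper-Pearson upper limit per arm: 1 − 0.025^(1/22) = 15.4%.
- Newcombe: the Wilson upper limit is z²/(n + z²) = 3.8415/25.8415 = 14.9%, giving ±14.9 points.
- Miettinen-Nurminen: at difference δ the restricted estimates are δ and 0, so δ² = z²·[δ(1−δ)/22]·(44/43). With k = 3.8415 × 2/43 = 0.1787, δ = k/(1+k) = 15.2 points, giving ±15.2.
- Miettinen-Nurminen stratified over two domains of 11 vs 11: k = 3.8415/21 = 0.1829, giving ±15.5.

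**One event, 0/22 vs 1/22.** Wald: −4.5 ± 1.96 × 4.44 = −13.2 to +4.2 points. Newcombe: −21.8 to +10.8. Miettinen-Nurminen: −22.1 to +11.0.

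**An illustrative domain, 0/11 vs 3/11.** Wald: −53.6 to −1.0, which excludes zero. Newcombe: −56.6 to +4.0. Fisher p = 0.21.

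**Coverage at 22 vs 22.** This is the sum, over all pairs of event counts, of the binomial probability of each pair whose interval contains the true difference. Miettinen-Nurminen (MN) is unstratified here.

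| True rates | P(0 vs 0) | Wald | Wald, given ≥1 event | MN | Newcombe |
|---|---|---|---|---|---|
| 1% vs 5% | 25.9% | 73.1% | 98.7% | 99.6% | 99.9% |
| 2% vs 5% | 20.7% | 76.7% | 96.8% | 99.4% | 99.7% |
| 2% vs 10% | 6.3% | 88.7% | 94.7% | 98.1% | 99.0% |
| 5% vs 10% | 3.2% | 87.4% | 90.3% | 96.9% | 98.3% |

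At 1% vs 5%, for example, P(0 vs 0) = (0.99 × 0.95)²² = 25.9%. That single outcome makes up 25.9 of the 26.9 points by which Wald falls short of 100%. At 5% vs 10% it makes up only 3.2 of 12.6.

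Wald is adequate elsewhere: 99.9% (2% in both arms), 98.5% (5% in both), 95.7% (10% in both) and 94.7% (10% vs 20%).

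With an uneven split, Wald coverage in the four tabulated scenarios is 75%, 80%, 91% and 91% if the lower-rate arm has 20 subjects and the other 24. It is 64%, 75%, 87% and 86% if the lower-rate arm has 24 and the other 20.

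**The case against.** **The variant is not named.** A continuity-corrected Wald interval is also a normal approximation. At 0 vs 0 it gives ±4.5 points, (1/22 + 1/22)/2, and its coverage in the four scenarios is 100.0%, 99.9%, 92.9% and 96.4%. It stands that the 0 to 0 result and the Wald coverages assume no correction. But the SAP mentions none, the uncorrected form is the ordinary reading, and ±4.5 points is still far narrower than the ±15 of the score-type intervals.

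**The failure is mostly one outcome.** Given at least one event, Wald is clearly low only at 5% vs 10%. SAP 3.4.1 says events were insufficient, not absent, and the exact per-arm intervals would still show uncertainty. This is right, and a zero-event rule alone would remove most of the shortfall at the two lowest pairs of rates. It would not mend 5% vs 10%, nor the narrow interval at 0 vs 1.

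**The replacement is not perfect.** At 0/22 vs 4/22, Miettinen-Nurminen (−38.8 to −1.7) excludes zero, as Wald does (−34.3 to −2.1), while Fisher p = 0.108; Newcombe (−38.5 to +0.2) does not. The coverages shown for Miettinen-Nurminen are unstratified, whereas the pooled comparison would be stratified. Both points stand. They bear on which score-type interval to choose, not on whether to keep Wald.

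**The SAP follows the protocol.** Protocol 7.7.1 already specified this interval, so its absence from SAP 3.4 is not itself an error. The mock-up tables are separate documents and could contain a rule; the SAP text does not.

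**Little hangs on it.** The trial is exploratory, stopped early, and has no decision rule tied to the interval. That limits the severity. It does not make a zero-width interval informative.

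**Conclusion.** The concern holds and should be fixed. The SAP's own reason for dropping logistic regression also undermines the one effect interval it keeps for the primary endpoint and the all-cause composite. With no events, that interval is 0 to 0 where score-type methods give about ±15 points at 22 per arm. At low, unequal rates its coverage is roughly 73% to 89% rather than 95%; at equal rates, or at 10% vs 20%, it is adequate.

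The zero-width result needs only the uncorrected form and no events in either arm. The other figures rest on the assumed 22/22 split and assumed rates. This is a reporting defect in the main estimate. It changes no sample size, endpoint or population.

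**What to change.** In SAP 3.2.3, and through it in 3.2.4, replace the normal approximation with one named score-type interval: Miettinen-Nurminen, stratified by domain for the pooled comparison and unstratified within a domain. Newcombe is an acceptable alternative. Add an entry to SAP 3.4 as a further change due to early termination. If treatment codes have already been opened, report the new interval as an addition and label it post hoc.

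The cost is one sentence, one entry and one programming change. Intervals will be wider and somewhat conservative at low rates (about 97% to 99.6% coverage for unstratified Miettinen-Nurminen in the four scenarios), and occasional disagreement with Fisher's test will remain. The choice between Fisher and CMH is a separate matter and need not be settled here.

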### **3.2.4 ANALYSIS OF SECONDARY EFFICACY ENDPOINT**

#### **The percentage of subjects with all cause hospitalization, emergency room visit or death during study period**

This endpoint will be analyzed in the same way as on primary endpoint.

#### **The percentage of subjects with improved pulmonary X-ray findings for pneumonia, relative to baseline or showing a return to normalcy**

Pneumonia status will be tabulated descriptively by visit. Percentage of 'Improved' or 'Normal' will be presented with the corresponding Clopper-Pearson exact 95% CI, and tested by using Fisher's exact test or Cochran-Mantel-Haenszel test.

